C.6.1. Determining the Initial CM Reinforcement Schedule. Building upon our pilot findings, we will use an escalating reinforcement schedule (see Table 1), such that each subsequent day of abstinence will be reinforced with a greater amount of money; however, to ensure that participants are not motivated to achieve sustained abstinence, we will program our CM schedule such that participants will be able to use cannabis one day each week without penalty. That is, there will be 1 “free” day per week when participants will not be penalized for using cannabis. This procedure will help to ensure there is an upper limit on reduced use, as our goal is to motivate participants to substantially reduce their use, but not to the point that they achieve sustained abstinence. Participants will earn \$10.00 for their first day of abstinence. Each subsequent day of bioverified abstinence/free day will result in participants’ compensation increasing by \$1.00. We also considered use of a *reset contingency*. Reset contingencies are designed to promote sustained abstinence because any post-abstinence substance use results in the level of reinforcement being reset to the initial (i.e., day 1) amount. While we have used reset contingencies successfully in the past, we have elected to not use a reset contingency in this study because our goal is to promote reduced use, not sustained abstinence. We have also elected to

increase (relative to our pilot) the amount of money that participants can receive to increase the likelihood that a majority (i.e., $\geq 50\%$) of participants will decrease their use by 50% or more.

| Table 1. R21 phase potential payment schedule with “free day” allowance | | | | | | | | | |
|---|------|---------------|--|----------|----------------------------|--|------------------|---------------|--|
| Week | Day | Saliva videos | (Regardless of use) Daily Saliva Video Uploads | Smoking? | Daily Saliva Video Uploads | Explanation | Total | Running Total | |
| Week 1 & 2 (Ad Lib) | 1-14 | 1 | \$2.50 | As Usual | No Bonus yet | \$7.50 (\$2.50 per video) payment for uploading saliva testing videos (regardless of cannabis use). \$5 for providing a self-initiated reading. | \$12.50 each day | 175.00 | |
| | | 2 | \$2.50 | As Usual | | | | | |
| | | 3 | \$2.50 | As Usual | | | | | |
| | | SI* | \$5.00 | As Usual | | | | | |

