| | | 2 | \$2.50 | No | | | | | |
| 54 | 1 | \$2.50 | Yes | | \$49.00 | | \$54.00 | \$1520.00 | |
| | | 2 | \$2.50 | Yes | | | | | |
| | 55 | 1 | \$2.50 | No | \$50.00 | | \$55.00 | \$1575.00 | |
| | | 2 | \$2.50 | No | | | | | |
| 56 | 1 | \$2.50 | No | | \$51.00 | | \$56.00 | \$1631.00 | |
| | 2 | \$2.50 | No | | | | | | |

only asked to respond to two daily alarms (instead of three). Note, this decreases the potential amount of money earned.

Seventy-two participants will be randomized using a 2:1 allocation ratio to either the Reduced Use

Condition (n = 48) or a Control Condition (n = 24). Inclusion of a control group will allow clear inferences to be drawn regarding the effects of reduced cannabis use on functional outcomes. Study participation will entail completion of the baseline assessment, completion of the 8-week EMA study, and completion of the 8-week follow-up assessment.

D.2. R33 Inclusion/Exclusion Criteria and Recruitment

Timeline

The final inclusion/exclusion criteria for the R33 phase of project will be identical to the R21 inclusion/exclusion criteria with one exception: Participants who are found to meet criteria for bio-verified sustained abstinence (i.e., all of their saliva tests are negative during the 6-week experimental phase of the study) will be excluded from the statistical analyses to ensure that there is an upper limit on reduced use. Thus, we will exclude any participants who achieve sustained abstinence to ensure that any improvements in functioning observed among participants in the experimental condition are not being driven by inclusion of a subset of participants who achieve sustained abstinence. Please also note that we can exclude up to 12 of the 72 enrolled participants from the statistical analyses (remaining N = 60) and still be adequately powered to conduct all of the proposed analyses.

[figure not shown]
D.3. Diagnostic Reliability and Training of Clinical Interviewers

Interviewers will be trained to conduct the interviews using our standardized laboratory procedures, including rating videotaped interviews and participation in ongoing weekly supervision. These procedures have produced consistently high interrater reliability, with Fleiss' kappa values ranging from .92-.94 in previous studies (Kimbrel, Newins et al., 2017; Kimbrel, Calhoun et al., 2014).

D.4. Participant Reimbursement

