Eligible participants will be trained in the EMA procedures following established procedures at the end of the baseline assessment (Beckham, Calhoun 2013). Participants will then practice with the electronic diary at home for 24 hours. Once the training period is complete, participants will complete an 8-week EMA study in which they will carry the diaries with them on a daily basis. The first 2 weeks of the EMA study will involve daily assessments of cannabis use and participants' functional outcomes during the *ad lib* period to establish baseline patterns of use. During the *ad lib* period, participants will also be asked to perform self-initiated diary readings when they begin cannabis use. When participants begin the diary reading, the phone will set an alarm for 60 minutes later. When the alarm sounds, the participant will use a saliva test kit and upload the readings. Participants will be paid \$5 once per day if they begin a self-initiated reading on that day. On day 15, participants in the Reduced Use Condition ($n = 48$) will begin reducing their cannabis use through participation in the mobile CM for cannabis protocol, whereas participants in the Control Condition ($n = 24$) will receive non-contingent payments based on the mean of two yoked participants' earnings. All participants will continue to provide EMA assessments of their functional outcomes during the 6-week experimental period so that we can study the impact of reduced cannabis use on functioning. Electronic diary data stored on the smart phone are encrypted at rest. Data will be downloaded from the smart phones to duhsnas-pri\dusom_psych\private\irb\[name]\Marijuana.

Table 3. Description and Timing of In-Person Assessments

| MEASURE | DESCRIPTION | BL | End of ad lib | 8-wk |
|--|---|----|----------------------|------|
| Demographic Assessment | PhenX (Hamilton et al., 2011) protocols will assess age (#010101), race (#010601), ethnicity (#010501), gender (#010700), and sexual orientation (#101401). | X | | |
| Structured Clinical Interview for DSM-5 (First et al., 2015) | Will be used to diagnose CUD and other psychiatric disorders based on DSM-5 criteria in order to determine study eligibility and characterize sample. | X | | |
| Columbia Suicide Severity Rating Scale (Posner et al., 2011) | State-of-the-art interview that assesses the full continuum of suicidal behavior. Will be used to determine study eligibility and assess suicidal behavior. | X | | X |

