To examine the effect of reduced cannabis use on functioning assessed with EMA, day-by-day outcome variables will be modeled *via* MLM as a function of treatment group (Level 2), week (Level 1; with the two baseline weeks treated as a single week), and treatment-by-week interactions. Daily consumption (total equivalent number of joints/gram consumed and total potency; Level 1) will be examined as potential covariates. Linear and quadratic time effects will be explored. Week-by-week effects of cannabis reduction will be examined in separate models. We will also examine the effects of reduced use by modeling day-by-day and week-by-week outcomes as a function of week-by-week reductions in cannabis, independent of treatment group. Linear MLM will be used to model normally distributed outcome variables *via* PROC MIXED. Generalized linear MLM will be used to model dichotomous and otherwise non-normally distributed outcome variables *via* PROC GLIMMIX.

E.4. Supplementary Aim.

To examine whether reduced cannabis use moderates or is moderated by other factors (e.g., sex differences), the models examined in Hypotheses 1a and 1b will be modified to include potential Level-1 (e.g., day-to-day craving, sleep) and Level-2 (e.g., sex, baseline cannabis use, self-efficacy) predictors as well as their interactions with week-by-week change in cannabis use. For instance, to determine whether a week-by-week reduction in cannabis use moderates the association of day-by-day cannabis use (or abstinence) with daily working memory, whether or not participants used cannabis that day (Level 1) will be added as a predictor of working memory as will its interaction with week-by-week change in frequency or quantity of cannabis use. This particular model could thus determine whether cannabis users demonstrate greater cognitive functioning on abstinent days when they reduce their cannabis use.

E.5. Power Calculations.

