Power calculations are based on Hypotheses 1a and 1b and were performed with Power Analysis and Sample Size software (PASS, Version 12: NCSS LLC, Kaysville, Utah). We conservatively estimate that as many as 12 participants could potentially need to be excluded due to sustained abstinence, leaving a minimum of 60 participants available for analysis. The corresponding analyses make use of multilevel data with a total sample of up to 3,360 records (60 participants X 56 daily observations). Because there will only be 7 unique estimates per participant of week-to week change in frequency of cannabis use, a conservative minimum estimate of the effective sample size is 420 (60 participants X 7 weekly

observations). Although these observations are non-independent given clustering within participants, hence the use of MLM, accounting for variation between participants will reduce the error variance in the dependent variables. Thus, the effective sample size will very likely exceed 420. An effective sample size of 420 has 90% power to detect small-to-medium treatment effects equivalent to Cohen's $d = 0.30$ or associations equivalent to $r = .16$.

References

Adkisson, K., Cunningham, K.C., Dedert, E.A., Dennis, M.F., Calhoun, P.S., Elbogen, E.B., Beckham, J.C., & Kimbrel, N.A. (manuscript under review). Cannabis use disorder and post-deployment suicide attempts in Iraq/Afghanistan-era veterans.

Babor TF, de la Fuente JR, et al., 1989. AUDIT The Alcohol Use Disorders Identification Test: Guidelines for use in primary health care (WHO/MNH/DAT 89.4). Geneva, Switzerland.

Beckham, J.C., Adkisson, K.A., Hertzberg, J., Kimbrel, N.A., Budney, A.J., Stephens, R.S., Moore, S.D., & Calhoun, P.S. (manuscript under review). Mobile contingency management as an adjunctive treatment for co-morbid cannabis use disorder and cigarette smoking.

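### Excluding full abstainers after randomisation means the treatment-by-week contrast no longer compares the arms as randomised

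*Combined protocol and SAP*

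**What the plan says.** Section D.1 randomises 72 participants, 48 to the Reduced Use Condition and 24 to the Control Condition. It justifies the control arm as follows: "Inclusion of a control group will allow clear inferences to be drawn regarding the effects of reduced cannabis use on functional outcomes".

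Section D.2 adds an exclusion that works at the analysis stage. A participant counts as sustained-abstinent if "all of their saliva tests are negative during the 6-week experimental phase of the study", and D.2 states that "we will exclude any participants who achieve sustained abstinence to ensure that any improvements in functioning observed among participants in the experimental condition" are not due to such participants. No analysis is exempted. Section E.5 builds the rule into the sample size: "as many as 12 participants could potentially need to be excluded due to sustained abstinence", which leaves 60.

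Under D.6, CM begins on day 15 in the Reduced Use arm, while controls "will receive non-contingent payments based on the mean of two yoked" participants' earnings.

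Section E.3 lists two kinds of model for Hypotheses 1a and 1b. The first takes daily outcomes "as a function of treatment group (Level 2), week (Level 1; with the two baseline weeks treated as a single week), and treatment-by-week interactions". The second takes outcomes "as a function of week-by-week reductions in cannabis, independent of treatment group".

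Sections E.1 to E.5 contain no analysis of all randomised participants and no sensitivity analysis that retains the abstainers.

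**The concern.** The rule appears under eligibility criteria, but it depends on what participants do after randomised treatment has begun, and on the very behaviour that CM is meant to change. Entry requires cannabis use on at least 40 of the past 90 days (C.3), and only one arm is paid for abstaining. It is a fair inference that nearly all exclusions would come from the CM arm. The wording covers both arms, however, and the documents give no split.

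Control participants who would have abstained fully under CM cannot be identified, so they stay in the comparison while their CM counterparts leave it. The group contrast is then no longer protected by randomisation, which is the protection D.1 relies on.

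Two limits apply. The ad lib baseline is in the model, so stable differences in level between abstainers and others cancel, and only differences in trajectory cause bias. The second E.3 model is observational in any case. There the rule narrows the exposure range but breaks nothing.

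**Working it through.** **The plan's own figures.** 72 − 12 = 60 and 60 × 7 = 420, as E.5 states. Treating the 420 as independent, power for r = .16 is 90.9%, which agrees with the stated 90%. For d = 0.30, two-sided, it is 86.7% with equal groups and 85.4% with a 36:24 split, which does not agree. That mismatch is a separate matter, and nothing below depends on it.

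**Inputs from the documents.** Arms of 48 and 24 and a ceiling of 12 exclusions (D.1, D.2); two-sided alpha of .05 (section E).

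**Assumptions not in the documents.** All k exclusions are in the CM arm. Those excluded are the top fraction f = k/48 on a normal latent trait. That trait correlates |r| = 0.2 to 0.5 with functional change. CM has no true effect on the outcome. The outcome is a single change score per participant, not the full multilevel model.

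**Formulas**, in units of the participant-level SD of change:

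- Shift in the mean of the retained CM arm: b = |r| × φ(z)/(1 − f), where z is the 1 − f normal quantile.
- Standard error of the between-arm difference: SE = √(1/(48 − k) + 1/24).
- Two-sided error: Φ(−1.96 + b/SE) + Φ(−1.96 − b/SE).

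Worked case, k = 12: f = 0.25, z = 0.674, φ(z) = 0.318, and 0.318/0.75 = 0.424. With |r| = 0.5, b = 0.212. SE = √(1/36 + 1/24) = 0.264, so b/SE = 0.80 and the error is 12.7%.

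| Excluded (k) | φ(z)/(1 − f) | Shift b, SD | SE, SD | b/SE | Two-sided error |
|---|---|---|---|---|---|
| 2 | 0.093 | 0.02–0.05 | 0.252 | 0.07–0.18 | 5.1–5.4% |
| 4 | 0.167 | 0.03–0.08 | 0.254 | 0.13–0.33 | 5.2–6.3% |
| 6 | 0.235 | 0.05–0.12 | 0.256 | 0.18–0.46 | 5.4–7.5% |
| 12 | 0.424 | 0.08–0.21 | 0.264 | 0.32–0.80 | 6.2–12.7% |

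**Simulation checks.** With 20,000 trials per setting and a t test on one mean per participant, type I error was 5.2% (k = 4, r = 0.2), 6.7% (k = 4, r = 0.5), 6.5% (k = 12, r = 0.2) and 13.1% (k = 12, r = 0.5). With all 72 kept it was 4.8 to 5.2%. A second simulation of 8,000 trials per setting let the trait shift baseline level as well and analysed change from baseline. At k = 12 and r = 0.5 it gave a bias of −0.202 SD and 12.8% rejection. With everyone kept, bias was within 0.006 of zero and rejection was 4.6 to 5.0%.

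**Precision.** With all 72, SE = √(1/48 + 1/24) = 0.250, against 0.264 with 36:24. The variance ratio is 0.0625/0.0694 = 0.90, so keeping everyone gives 10% lower variance.

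**The case against.** The exclusion is deliberate, disclosed and tied to the sponsor's question, which is whether reduced use helps without sustained abstinence. In C.6.1 the sponsor writes that "our goal is to motivate participants to substantially reduce their use, but not to the point that they achieve sustained abstinence". An analysis of everyone randomised estimates the effect of being offered CM, abstainers included, which is a different question. E.3 does not rank its models, and the hypotheses are worded as associations, which fits the second model better.

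Exclusions may also be few. Every test over six weeks must be negative, one day of use per week carries no penalty, and none of the four pilot participants reached a 100% reduction (range 18 to 93%, B.5). Twelve is an allowance, not a forecast.

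Finally, a two-sided error rate hides direction. If full abstainers improve more than others, removing them makes CM look worse. At k = 12 and r = 0.5 the 12.7% is then about 12.4% false harm and 0.3% false benefit. If CM truly helps, the result is attenuation.

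Much of this stands as a limit on size. The number excluded, their split by arm and the direction of bias are unknown, and the correlation is assumed. Four pilot participants are weak evidence, though, and C.6.1 raises payments above the pilot's. None of it restores the comparison. Pre-specifying a rule does not remove the selection it causes, and taking abstainers out of mainly one arm does not answer the sponsor's question with randomisation intact. The group contrast is one of the planned tests, and D.1 rests its causal claim on the control arm.

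**Conclusion.** The concern holds and should be fixed before analysis. As written, the treatment-by-week contrast does not compare the groups as randomised, and no planned analysis does. This follows from the text and does not depend on the illustration. The distortion is small with two to four exclusions and material near the ceiling of 12. Those sizes rest on the assumed one-sided exclusions, the assumed correlation of 0.2 to 0.5 and the simplified change-score model. The sign could go either way, so the result cannot be called conservative. The point is confined to the group contrast and does not extend to the model that ignores treatment group.

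A lesser gap goes with it. The plan does not say how missing tests count, so read literally a participant with a handful of uploads, all negative, would be dropped as a sustained abstainer.

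**What to change.** - Run the treatment-by-week models for Hypotheses 1a and 1b on all randomised participants with available EMA data, whatever their cannabis use, and name this the main between-group result.
- Keep the exclusion of sustained abstainers as a labelled sensitivity analysis of that contrast, and in the reduction model that ignores treatment group, where the question of benefit without abstinence belongs.
- For that classification, state a minimum share of scheduled tests and say how missing tests count. Table 2 implies 2 × 42 = 84 tests. D.6.1 still describes three alarms a day, so the two sections need to be reconciled before the denominator is fixed.
- Report the number excluded by arm.

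The cost is protocol and SAP wording and one more model run per outcome. D.6 has all participants continue EMA through the experimental period, so no new data are needed and no sample is lost. The price is that the main group estimate will include some full abstainers. The reading of reduction without abstinence will then rest on the sensitivity and reduction-exposure analyses.

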to stress, trauma, and coping strategies. Participants will be informed about these new study procedures verbally, and the study team member who informs them will provide a note-to-fil indicating so. Participants can refuse to complete these measures. We will ask ongoing participants to complete these measures at their next study visit or follow-up session. When study enrollment begins again, participants will complete these measures at the screening session. We are adding the CAIR Pandemic Impact Questionnaire (Lang, 2020; https://www.nlm.nih.gov/dr2/CAIR-PIQ_scoring.pdf), and another measure, COVID Core Questions, with variables of interest. If a participant endorses any item marked with an asterisk on the COVID Core Questions measure, we will ask them to complete a PTSD Checklist 5 related to that specific event. Finally, we have added a measure designed to evaluate participants' satisfaction with remote study procedures.

E. DATA ANALYSIS PLAN

Multilevel modeling (MLM) will be used to analyze the EMA data. MLM is a technique for analyzing repeated observations of data across multiple individuals. Unlike repeated-measures ANOVA, MLM can incorporate time-varying (Level-1) and time-invariant (Level-2) predictors. MLM can also accommodate imbalanced data and unequal variances. The main conclusions drawn from this study will be based on the pre-specified hypotheses, which will be tested with two-sided statistical tests at an alpha of .05. Analyses will be performed with SAS for Windows (Version 9: SAS Institute, Cary, NC).

E.1. Missing Data.

Although we do not anticipate much missing baseline data, we do anticipate missing values in the EMA data. MLM procedures, which will be used to analyze H_{1A}, H_{1B}, and the supplementary aim, are based on maximum likelihood estimation and use all available data. As such, MLM can accommodate data missing at random. Missing data will be examined to determine whether missingness is random or systematically associated with baseline variables. Those baseline parameters associated with missingness will be covaried. If data are suspected to be missing not at random (i.e., only certain values are likely to be missing), multiple imputation will be used to analyze non-random patterns of missing EMA data (Schafer & Graham, 2002).

E.2. Electronic Diary Compliance and EMA Data Reduction.

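### D.2 claims adequate power for every proposed analysis at N = 60, but E.5 sizes only Hypotheses 1a and 1b, and nothing supports the claim for the E.4 moderator interactions

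*Combined protocol and SAP*

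**What the plan says.** D.2 (R33 inclusion/exclusion criteria) removes participants with bio-verified sustained abstinence from the analyses. It then notes that up to 12 of the 72 can go, leaving 60, "and still be adequately powered to conduct all of the proposed analyses". No analysis is excepted.

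E.5 is the only power section. It opens with "Power calculations are based on Hypotheses 1a and 1b". It takes 60 participants times 7 weekly values as a minimum effective sample size of 420 and states: "An effective sample size of 420 has 90% power to detect small-to-medium treatment effects", namely d = 0.30, or an association of r = .16. The opening of section E says the pre-specified hypotheses will be "tested with two-sided statistical tests at an alpha of .05".

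E.4 (Supplementary Aim) extends the 1a/1b models with further Level-1 and Level-2 "predictors as well as their interactions with week-by-week change in cannabis use". Its examples are craving and sleep (Level 1) and sex, baseline use and self-efficacy (Level 2). The Specific Aims present this as exploration.

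Drugged driving belongs to Hypothesis 1b. E.2 reduces it to a daily yes/no indicator, and E.3 sends dichotomous outcomes to a generalized linear mixed model. E.5 gives no event rate and no odds ratio.

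**The concern.** The moderator analyses in E.4 are among the proposed analyses, so D.2 covers them on its face. E.5 does not. An interaction is usually estimated less precisely than the overall effect on the same data, so adequacy for 1a/1b cannot simply be extended to E.4. A similar gap exists inside 1b, because power for a binary outcome depends on how common the event is, and d and r do not carry that information.

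What is at stake is how results are read. If the plan says every analysis is adequately powered, a null sex or baseline-use interaction could be taken as informative when no calculation supports that. The sentence also reassures the reader that removing up to 12 randomised participants leaves every analysis intact.

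**Working it through.** **Inputs from the documents.** N = 72 − 12 = 60 (D.2); effective n = 60 × 7 = 420, power 90%, d = 0.30 or r = .16 (E.5); two-sided alpha .05 (E); 2:1 allocation (D.1). **Assumed, because the documents do not give them:** the moderator split, the meaning of an interaction of the same size, and the drugged-driving event rates.

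**1. E.5's own figures, treating the 420 records as independent.**
- r = .16: atanh(.16) × √417 = 3.296; Φ(3.296 − 1.960) = 90.9%. This reproduces.
- d = 0.30: Φ(0.30/√(1/n1 + 1/n2) − 1.960).
  - 1:1 (210/210): 0.30/0.0976 = 3.074, power 86.7%.
  - 2:1 (280/140): 0.30/0.1035 = 2.898, power 82.6%.
  - 36:24 participants, if all 12 exclusions fall in the Reduced Use arm (252/168): 3.012, power 85.4%.
- None of the d results is 90%. At 2:1 or 36:24 the figure comes close only one-sided (89.5%, 91.4%), contrary to the stated two-sided test.
- d needed for 90% two-sided: 3.242 × 0.0976 = 0.316 (1:1) or 3.242 × 0.1035 = 0.336 (2:1).

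**2. Two-level between-person moderator.** Let p be the share in one level. The standard error of the difference between the two subgroup effects is the main-effect standard error divided by √(p(1 − p)). If that difference equals the main effect, power = Φ(ncp × √(p(1 − p)) − 1.960), where ncp is the main-effect noncentrality.

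| Split | √(p(1 − p)) | From E.5's 90% (ncp 3.242) | From 82.6% (ncp 2.898) |
|---|---|---|---|
| 50:50 | 0.500 | 36.7% | 30.5% |
| 60:40 | 0.490 | 35.5% | 29.5% |
| 70:30 | 0.458 | 31.8% | 26.4% |

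For 90% power the interaction must be 1/0.500 = 2.0 to 1/0.458 = 2.18 times the main effect that itself has 90%. Equivalently, from E.5's own figure, the effective n must be 4.0 to 4.76 times larger, about 1,680 to 2,000. A continuous moderator gives the same 36.7% if the effects at +1 SD and −1 SD differ by the main effect.

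**3. The same question under another definition.** If the interaction term itself is taken to have a partial r of .16: atanh(.16) × √415 = 3.288; Φ(3.288 − 1.960) = 90.8%, about 91%.

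**4. Drugged driving.** d = 0.30 converts to an odds ratio of exp(0.30 × π/√3) = 1.72. I applied it as a reduction (odds multiplied by 1/1.72) with 280 vs 140 records and the unpooled two-proportion formula.

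| Assumed control event rate | 10% | 20% | 30% | 40% | 50% | 60% |
|---|---|---|---|---|---|---|
| Power | 27% | 46% | 60% | 69% | 74% | 75% |

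The fair comparator on this base is the 82.6% for a continuous outcome, not 90%.

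**The case against.** The strongest reply is that the low interaction figures depend on a definition the documents do not contain. E.5 offers r as well as d, and E.4's interactions involve a change score, for which r is a natural metric. On a partial r of .16 the power is about 91%. This stands: the 32% to 37% illustrates one case and is not a property of E.4. A reader might infer that all the moderators have about one-third power. The documents do not support that. Craving and sleep vary from day to day, baseline use and self-efficacy need not be dichotomised, and E.5 counts up to 3,360 daily records and treats 420 as a floor.

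A reader might also infer that the sponsor intends to read null interactions as absence of moderation, or that the power sentence is the reason for the exclusions. Neither is in the text. The aim is labelled supplementary and exploratory, the main conclusions are tied to the pre-specified hypotheses, and D.2's stated reason for the exclusions is to cap the degree of reduction. The power remark is an added note.

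On drugged driving, E.5 does claim to cover 1b, the outcome is daily while the calculation uses weekly records, and entrants are heavy users, so high event rates cannot be ruled out. The range is therefore wide, and part of its distance from 90% comes from E.5's d figure rather than from the outcome being binary.

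None of this supplies a power basis for E.4. An exploratory label explains why power was not calculated; it does not justify D.2's claim that power is adequate.

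**Conclusion.** The point holds as a matter of scope. D.2 asserts adequacy for all proposed analyses, while the plan demonstrates it, at most, for the effects sized in E.5. Low power for an exploratory aim is not a design fault; claiming adequate power for it without a basis is a fault in the statement.

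The size is conditional. It is roughly 37% to 32% from E.5's 90%, or 30% to 26% from 82.6%, for a two-level moderator split 50:50 to 70:30 with a subgroup difference equal to d = 0.30. It is about 91% if the interaction is a partial r of .16. For drugged driving it is about 27% to 75% over assumed control rates of 10% to 60%. All of these treat the 420 records as independent.

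E.5's d = 0.30 does not reach 90% under the plan's own two-sided test, so D.2 should not simply defer to E.5 as it stands.

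**What to change.** 1. Correct E.5: with 420 records taken as independent, 90% two-sided power needs d of about 0.32 (1:1) or 0.34 (2:1). State the allocation used and the independence assumption.
2. Limit D.2's sentence to the Hypothesis 1a/1b effects sized in the corrected E.5.
3. State in D.2 or E.4 that the Supplementary Aim is exploratory with no power claimed, so a null interaction is not evidence of no moderation.
4. If a figure is wanted, give the detectable interaction with its definition and moderator split. For a two-level moderator it is at least twice the corrected main effect: 0.316/0.500 = 0.63 (1:1) or 0.336/0.500 = 0.67 (2:1) at a 50:50 split, and larger for unequal splits. Give the detectable odds ratio for drugged driving with its assumed event rate.

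This changes wording only; sample size, procedures and models are unaffected. The cost is that the stated power claim becomes narrower.
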